### **Recruitment and Informed Consent**

Males will be recruited from the millennial generation (20-34 y), as males typically have a greater postprandial lipid response than females [16]. In general, Millennials are chosen as this population demographic has been demonstrated to have the greatest variation in meat intake [17]. Recruitment will occur via posters placed around the University of Auckland and using social media sites (Facebook™). Informed consent will be collected by research staff following participant's inquiry and provision of information.

### **Ethics and dissemination**

The trial has been granted ethical approval by the New Zealand Ministry of Health's Health and Disability Ethics Committees (Ref: 19/STH/226). All results originating from this study will be submitted for publication in scientific journals and presented at meetings.

### **Sample size calculation**

The principal biomarker for calculation of sample size is postprandial change in LCPUFA concentrations in plasma chylomicrons (namely 20:4 n-6, 20:5 n-3, 22:5 n-3, 22:6 n-3). We estimate a sample size of 29 would enable the detection of a smallest worthwhile change of 0.5 mmol/L from baseline to 4 hours post meal consumption [19]. Pooled published data indicate an increase of ~3.9 mmol/L ( $\pm 2.8$  mmol/L) in chylomicron fatty acids post meal consumption. An effect size of 0.2 is used to calculate the smallest worthwhile effect. Recruitment will continue until 29 men have successfully completed the trial.

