## **METHODS/DESIGN**

### **Study Setting**

The trial will be conducted at the University of Auckland Clinical Research Centre. The study is a randomised crossover trial to capture biological difference in postprandial nutrient dynamics. Research subjects will act as their own controls and will consume each meal on a separate occasion in random order. The study compares exemplars of pasture-fed New Zealand beef, grain-finished New Zealand beef, New Zealand lamb and a plant-based meat analogue. The pasture-fed beef was obtained from Angus Steers that had been fed exclusively on pastures (ryegrass and white clover mix) whereas the grain-finished beef was Angus steers that had been finished for an average of 122 days on a maize silage, barley wheat and straw ration. Marble score (3-4/9 on the Australian Grading System) [15] and pH (average 5.5) of the meat were consistent between production systems. The lamb will be sourced from New Zealand. The meat analogue has been selected from commercial varieties on the basis of its macronutrient profile (protein and fat) and appearance to best match that of meat.

The digestion and metabolism of key nutrients will be measured immediately after the ingestion of a single meal. This experimental setting will also be used to examine some subjective qualities of the meal experience, such as satisfaction score (i.e., liking, satisfaction, enjoyment, satiety, appetite) and gastrointestinal score (i.e., comfort, fullness, bloating, rumbling, flatulence, faecal urgency, diarrhoea).

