## Outcomes (Primary and Secondary)

Following the consumption of a single meal:

Primary outcome variable

- Change in LCPUFA (18:2 n-6, 18:3 n-3, 20:4 n-6, 20:5 n-3, 22:5 n-3, 22:6 n-3) concentrations in the chylomicron fraction over 4 hours. Difference in the change between pasture-, grain-beef, lamb and plant-based alternative meat meals.

Secondary outcome variables

- Differences in other fatty acid (14:0, 16:0, 16:1 n-7, 18:0, 18:1 n-9, others) concentrations in the chylomicron fraction over 4 hours.
- Differences in the plasma amino acid (isoleucine, leucine, valine, histidine, lysine, methionine, phenylalanine, threonine, alanine, arginine, asparagine, aspartic acid, glutamic acid, glutamine, glycine, proline, serine, tyrosine, 3-methylhistidine, citrulline, hydroxyproline, ornithine, taurine, others) concentrations over the 4 hours.
- Differences in plasma neurotransmitter concentrations (phenylethyl amine, 3,4-dihydroxyphenylalanine, dopamine, 3-methoxytyramine, 3,4-dihydroxyphenylacetic

acid, homovanillic acid, norepinephrine, 3,4-dihydroxyphenylglycol, 3-methoxy-4-hydroxyphenylglycol, normetanephrine, epinephrine, metanephrine, vanillylmandelic acid, tryptophan, kynurenine, 5-hydroxytryptophan, serotonin, 5-hydroxyindoleacetic acid, alpha-aminobutyric acid, gamma-aminobutyric acid).

- Differences in minerals and haemoglobin concentrations.
- Change in inflammatory markers (TNF $\alpha$ , IL-1, IL-6, IL-8, IL-10, IL-13, hs CRP).
- Digestive differences based on genetic profile.
- Differences in subjective experience to the meal including fullness, satisfaction, gastrointestinal comfort scores among pasture-, grain- and plant-based alternative meat meals.
- Qualitative differences in the participant's opinions regarding future red meat consumption ("Participant insights").
- Adverse events, count score differences between meals.

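### The claim that 29 men can detect 0.5 mmol/L does not follow from the figures printed with it, and it does not size the between-meal comparison in the primary outcome

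*Protocol*

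**What the plan says.** The protocol's Sample size calculation section bases the number on the postprandial change in plasma chylomicron LCPUFA, defined there as four fatty acids: "namely 20:4 n-6, 20:5 n-3, 22:5 n-3, 22:6 n-3". It states that "a sample size of 29 would enable the detection of a smallest worthwhile change of 0.5 mmol/L from baseline to 4 hours". In support it says "Pooled published data indicate an increase of ~3.9 mmol/L", followed by ±2.8 mmol/L with no label saying which statistic that is. The sentence ends, and the next one follows, with "in chylomicron fatty acids post meal consumption. An effect size of 0.2 is used to calculate the smallest worthwhile effect". The section closes with the recruitment rule: "Recruitment will continue until 29 men have successfully completed the trial". It gives no alpha, power, within-person SD or correlation.

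The Outcomes section defines the primary outcome in two parts. The first is "Change in LCPUFA (18:2 n-6, 18:3 n-3, 20:4 n-6, 20:5 n-3, 22:5 n-3, 22:6 n-3) concentrations in the chylomicron fraction over 4 hours", which is six fatty acids. The second is "Difference in the change between pasture-, grain-beef, lamb and plant-based alternative meat meals". Study Setting says that the crossover is meant "to capture biological difference in postprandial nutrient dynamics", with each man as his own control. Trial Design adopts a non-inferiority framework.

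**The concern.** Four things do not fit together.

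1. The 0.2 and the 2.8 define how large a worthwhile effect is. They do not say how precisely 29 men would measure it, so the claim of detection has no visible basis.
2. The effect named is a change from baseline after a meal. The comparison that a crossover of four meals exists to make is the difference in that change between meals. Its precision depends on the SD of the within-person difference, which is not given.
3. The variable changes from four fatty acids in the sizing to six in the outcome (18:2 n-6 and 18:3 n-3 are added). The ±2.8 belongs to chylomicron fatty acids in general, so it is the spread of neither list.
4. Detecting a change is not the same aim as showing non-inferiority.

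At stake is the reading of the result. Recruitment stops at 29 completers on the strength of this sentence, and 0.5 mmol/L is the only detectability figure in the protocol. A reader who meets a finding of no difference, or of non-inferiority, between the analogue and a meat meal would take it that a 0.5 mmol/L difference could have been seen. Nothing printed supports that.

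**Working it through.** **Inputs.** From Sample size calculation: n = 29 completers, target 0.5 mmol/L, rise 3.9 mmol/L, ±2.8 mmol/L (read as an SD, an assumption), effect size 0.2. From Outcomes: four meals, hence 4 × 3 / 2 = 6 possible pairs. Assumed because not stated: two-sided 5%, 80% power, a paired t-test (noncentral t, 28 degrees of freedom) and, where six pairs are considered, a Bonferroni correction.

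**Step 1: the target.** 0.2 × 2.8 = 0.56 mmol/L, close to the printed 0.5. Conversely 0.5 / 2.8 = 0.179. The two figures therefore reproduce the target, approximately.

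**Step 2: the 29.** Taking 2.8 as the SD of the change tested:

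| Effect (mmol/L) | Effect / 2.8 | Power with 29 | Men for 80% power |
|---|---|---|---|
| 0.5 | 0.179 | 15% | 249 |
| 0.56 | 0.200 | 18% | 199 |
| 3.9 (the whole rise) | 1.39 | over 99% | 7 |

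A one-sided 5% test needs 196 men for 0.5 mmol/L. At 90% power, two-sided, it is 332. Smallest-worthwhile-change formulas give roughly 66 to 120. Reading 2.8 as a variance or as a 95% interval half-width gives 42 to 90. None of these gives 29.

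**Step 3: the between-meal difference.** If 2.8 were the between-person SD of the change after each meal and ρ the correlation between meals within a man, then SD of difference = 2.8 × √(2(1 − ρ)). The protocol gives no ρ, so a range is shown for a 0.5 mmol/L difference:

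| ρ | SD of difference | Power, one pair | Power, six pairs (Bonferroni) |
|---|---|---|---|
| 0.5 | 2.80 | 15% | 4% |
| 0.8 | 1.77 | 31% | 11% |
| 0.9 | 1.25 | 55% | 27% |
| 0.95 | 0.89 | 84% | 58% |

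These rows illustrate sensitivity and do not estimate the trial's power, because 2.8 is not an LCPUFA spread. With a smaller assumed SD of change of 0.9 mmol/L, power for one pair is 82% at ρ = 0.5 and 96% at ρ = 0.7. With 1.4 mmol/L it is 46% and 67%.

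**Step 4: what 29 men can do, without a borrowed SD.** In units of the SD of the within-person difference:

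- Detectable difference at 80% power: 0.54 SD (one pair), 0.69 SD (six pairs, Bonferroni).
- Half-width of the 95% interval: t(0.975, 28) / √29 = 0.38 SD, or 0.53 SD with Bonferroni over six.
- Non-inferiority margin excluded with 80% power if the true difference is zero: 0.54 SD (one comparison, one-sided 2.5%), 0.63 SD (three, Bonferroni), 0.69 SD (six).

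**Step 5: what the 0.5 claim would need.** 0.5 / 0.539 = 0.93 mmol/L as the SD of the difference for one pair, and 0.5 / 0.689 = 0.73 mmol/L for six. If each meal's SD were 2.8, these correspond to ρ = 1 − (0.93 / 2.8)² / 2 ≈ 0.945 and, likewise, about 0.966. The protocol gives neither an SD of the difference nor a correlation.

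**The case against.** The strongest reply is that 29 can be reached by a standard between-meal calculation. A repeated-measures ANOVA over four meals with f = 0.2, correlation 0.6 and 5% alpha has 80.7% power at n = 29, and 0.2 is a printed figure. The number may therefore have been derived for the right comparison and then described badly. It stands that 29 is not an impossible number, and nothing here shows it to be inadequate. But the correlation, alpha and power in that route are not printed, and it does not rescue the sentence. With SD 2.8, f = 0.2 means an SD of the four meal means of 0.56 mmol/L. If two meals sit midway, the extremes are 2 × √2 × 0.56 = 1.58 mmol/L apart, which is not a 0.5 mmol/L change from baseline.

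It can also be said that the mmol/L power figures use a 2.8 that is itself disputed, and that six pairs with Bonferroni is an assumption, since multiplicity may be settled in a statistical analysis plan that is not shown. Both points are fair. Those figures are conditional, and a smaller LCPUFA spread would raise power, as step 3 shows. The conclusion does not depend on them.

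Finally, one may call this incomplete reporting that a later plan could fill. An analysis plan can supply a margin or a model. It does not remove a detectability figure that the protocol states, or the conflict between four and six fatty acids.

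**Conclusion.** The concern holds. The printed figures lead to the target of about 0.5 mmol/L but not to 29 men. The claim is about a change from baseline in a four-fatty-acid variable, whereas the primary outcome has six fatty acids and includes a between-meal comparison whose sizing is not shown. The effect on power cannot be derived from the protocol. It would be about 15% for 0.5 mmol/L if 2.8 were the SD of the paired quantity tested, and could be above 80% if the SD of the difference were below about 0.93 mmol/L. What can be said firmly is that 29 completers detect 0.54 SD of the within-person difference for one pair, or 0.69 SD for any of six pairs with Bonferroni, at an assumed 80% power and two-sided 5%. This needs correcting because the sentence sets the recruitment stop and is the only yardstick a reader has for a null or non-inferior result.

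**What to change.** Keep 29 completers and change the text:

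1. Use one fatty-acid list in Sample size calculation and Outcomes.
2. Remove the 0.5 mmol/L claim unless an SD of the between-meal difference is documented for that LCPUFA variable at about 0.93 mmol/L or less (one named pair) or 0.73 mmol/L or less (six pairs, Bonferroni). These limits assume 80% power and two-sided 5%; recompute them for the alpha and power the sponsor adopts.
3. Otherwise state the detectable effect in SD units, under one framework.
   - If the aim is to detect differences, correct Trial Design and write, for example: *29 completers give 80% power to detect a between-meal difference in 4-hour LCPUFA change of 0.54 SD of the within-person difference for one pair at two-sided 5%, or 0.69 SD for any of six pairs with Bonferroni.*
   - If non-inferiority is kept, state a margin justified on its own grounds and write: *with a true difference of zero, 29 completers give 80% power to exclude a margin of 0.54 SD (one comparison, one-sided 2.5%), 0.63 SD (three, Bonferroni) or 0.69 SD (six).*
4. Convert to mmol/L only with a sourced within-person SD for the chosen variable.
5. Label the ±2.8: which statistic it is and which fatty acids it covers.

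The cost is one rewritten paragraph, one aligned list and possibly one corrected phrase in Trial Design. It needs no further participants, visits or assays. The drawback is a less favourable stated effect, or one given only in SD units until an LCPUFA SD is found.

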### **Randomisation and Blinding**

The design will be a single blinded crossover. Participants will consume each test meal in random order, using a computer-generated sequence, at least one week, but no more than one month, apart. The randomisation will be conducted centrally, with one research staff responsible for meal preparation aware of the allocation. Staff responsible for blood collection and analysis will be blinded to the intervention, as will participants.

Reminder text messages will be sent to participants to increase attendance to each of the four study appointments. Additionally, participants will receive financial compensation for partaking in the end of four assessment visits. Participants will have the right to withdraw from the study at any time. The principal investigator will have the right to discontinue participants' involvement in the study if they become ineligible or when significant protocol deviations occur. The data of participants who withdraw will be kept and might be used in exploratory analyses, unless the participant requests for the data to be deleted.

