### **Study Overview**

Two test meals will include the same cut and quality of pasture-fed New Zealand beef or grain-fed New Zealand beef of well-defined provenance, which has been specifically slaughtered, packaged and stored for this trial. The third test meal will be lamb meat that will be sourced from New Zealand as a representative sample. The fourth test meal will be a commercial plant-based meat alternative that best resembles in terms of appearance and macronutrient profiles.

Meals will include a 220 g raw serving of beef or lamb (approximately 160 g cooked), which is in line with the World Cancer Research Fund / International Agency for Research on Cancer recommendation on red meat consumption, which suggests limiting the weekly red meat consumption to 350-500 g cooked. A minimum quantity of 100 grams cooked meat is required to ensure adequate fat intake to allow assessment of post-meal lipid dynamics [19]. The test meals will be provided in the morning after an overnight fast. The meals will look identical in appearance and participants will not be told which meal they have received.

Saliva samples will be collected at one time prior to meal consumption (baseline). These samples will be sent for subsequent analysis at the Nutrigenomix Inc laboratory. The test analyses variations in 70 genes that impact nutrient metabolism, eating habits, weight management and body composition, food intolerances and physical activity. The accuracy of the genetic test results are between 99.7 – 100%.

Blood samples will be collected immediately prior to (baseline) and 60, 120, 180 and 240 minutes following the meal for serum and EDTA plasma. Bloods will be taken in the phlebotomy room in the research facility, by a phlebotomist using via an indwelling catheter. Blood samples will be processed and frozen at -80°C for subsequent analysis.

During this time of each visit, participants will remain in the research unit. Appetite, digestive comfort and palatability scores will be self-reported using manual questionnaires.

The SPIRIT reporting guidelines for the accurate documentation of clinical trial protocols has been followed [16]. See Table 1 for trial schedule.

**Table 2.** SPIRIT Chart. Schedule of enrolment, interventions, and assessments

TIMEPOINT	STUDY PERIOD									
	Enrolment	Allocation			Post-allocation					Close-out

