	-t1	0	tpre	t0	t30	t60	t120	t180	t240	+t1
ENROLMENT:										
Eligibility screen	X									
Informed consent	X									
Allocation		X								
INTERVENTION MEALS:										
Grain-fed Beef		Random order		X						
Grass-fed Beef		Random order		X						
Lamb		Random order		X						
Meat Alternative		Random order		X						
ASSESSMENTS:										
Amino acids			X			X	X	X	X	
Neurotransmitters			X			X	X	X	X	
Inflammatory Markers			X			X	X	X	X	
Chylomicron fatty acids			X			X	X	X	X	
Chylomicron Lipidomics			X						X	
Glucose/ Insulin			X			X	X	X	X	
Vitamins (ADEK)			X			X	X		X	
Vitamins (Bs)			X			X	X		X	
Haemoglobin/ Minerals			X			X	X	X	X	

Saliva genetic markers			X							
Questionnaire-Fullness			X	X	X	X	X	X	X	
Questionnaire-Digestive Symptoms			X	X	X	X	X	X	X	
Questionnaire-Palatability					X					
Questionnaire-Participant Insight										X

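### Withdrawers' data get at most an optional exploratory role, so the primary meal comparison reads as completers-only and sets aside usable within-man contrasts (low priority)

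*Protocol*

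**What the plan says.** Three parts of the protocol bear on this point.

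- **Withdrawals.** Under Randomisation and Blinding: "The data of participants who withdraw will be kept and might be used in exploratory analyses". The one exception is deletion at the man's request. The same paragraph lets the investigator discontinue men who become ineligible or have significant deviations, but does not say whether the data rule covers them.
- **Recruitment.** Under Sample size calculation: "Recruitment will continue until 29 men have successfully completed the trial". Men who leave are therefore replaced.
- **Design.** Under Study Setting: "Research subjects will act as their own controls". The primary outcome compares the change in chylomicron LCPUFA between meals. Trial Design declares a non-inferiority framework.

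Each visit stands alone as a measurement. Blood is drawn at baseline "and 60, 120, 180 and 240 minutes following the meal", and the row "Chylomicron fatty acids" in Table 2 is marked at all five times. The sample size is framed on the change "from baseline to 4 hours post meal consumption", which one visit supplies. The Measurements section has the chylomicron fraction separated within 6 hours, before anyone can know whether the man will finish all four meals.

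**The concern.** The sentence on withdrawers gives their data one use, which is both optional and exploratory. Read with recruitment to 29 completers, it points to a primary comparison made only in men who ate all four meals. That suits a crossover poorly, because a man with two or three evaluable visits contributes the same kind of within-man meal difference as a completer.

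Some withdrawal is foreseeable. Visits are "at least one week, but no more than one month, apart", so the three gaps between four visits span about three weeks to three months.

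Two things are at stake. The first is a little precision in a trial of 29 men. The second is selection, if leaving is related to how a man responded to a meal. Participants are blinded and cannot perceive a chylomicron response, so any such link would be indirect, for example through the "gastrointestinal score (i.e., comfort, fullness, bloating, rumbling, flatulence, faecal urgency, diarrhoea" items that the trial scores. Leaving the use of these data optional also leaves a choice open until results are known.

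**Working it through.** **The plan's own figure.** The planned 29 cannot be reproduced from the stated inputs. Reading ±2.8 as an SD and assuming two-sided 5% and 80% power, a paired calculation gives (2.8 × (1.960 + 0.842) / 0.5)² ≈ 246.2, so 247 men. With the effect size of 0.2 it gives 197. That is a separate matter; here 29 completers is taken as given.

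**Inputs**
- From the protocol: 29 completers, 4 meals, 5 samples per visit, mean change 3.9 and SD 2.8 mmol/L. The SD is for chylomicron fatty acids in general, not for the LCPUFA outcome.
- Assumed, with no source in the protocol: number of withdrawers *m*, visits each *k*, within-man correlation ρ (0.3-0.7), and any link between leaving and response.

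**Precision**

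Leaving period effects aside, with meals in random order, a man with *k* of 4 visits carries this share of a completer's information on a meal contrast:

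w(k) = (k/4) × [1 − c × (4 − k)/3], where c = ρ / (1 + (k − 1)ρ).

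At ρ = 0.5:
- k = 1: c = 0.5, w = 0.25 × 0.5 = 0.125
- k = 2: c = 0.333, w = 0.5 × 0.778 = 0.389
- k = 3: c = 0.25, w = 0.75 × 0.917 = 0.6875

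Variance relative to 29 completers alone is 29 / (29 + m·w). The last column is generalised least squares with period in the model and random meal orders.

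| Withdrawers | Meals each | Formula, ρ 0.5 | With period, ρ 0.3 / 0.5 / 0.7 |
|---|---|---|---|
| 1 | 2 | 29/29.389 = 0.987 | 0.985 / 0.986 / 0.987 |
| 1 | 3 | 29/29.688 = 0.977 | 0.976 / 0.976 / 0.977 |
| 2 | 2 | 29/29.778 = 0.974 | 0.971 / 0.973 / 0.975 |
| 2 | 3 | 29/30.375 = 0.955 | 0.952 / 0.953 / 0.954 |
| 5 | 2 | 29/30.944 = 0.937 | 0.931 / 0.936 / 0.940 |
| 5 | 3 | 29/32.438 = 0.894 | 0.889 / 0.891 / 0.893 |

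Five withdrawers with one meal each save 3% or less. Reductions in SE are about half the reductions in variance. Five men with three meals are worth 29/0.891 − 29 ≈ 3.5 extra completers; five with two meals, 29/0.936 − 29 ≈ 2.0.

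**Selection**

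The simulation used mean 3.9, SD 2.8 and ρ 0.5, with men leaving only after one designated meal (here the analogue) when it was not their last. The slope is the rise in log-odds of leaving per SD of lower response. Entries are bias in analogue minus meat (mmol/L), completers-only / mixed model on all visits.

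| Leaving depends on | Slope | 5% leave | 10% leave | 15% leave |
|---|---|---|---|---|
| Recorded response | 0.5 | 0.033 / −0.001 | 0.067 / 0.002 | 0.098 / 0.003 |
| Recorded response | 1 | 0.066 / 0.002 | 0.123 / 0.002 | 0.175 / 0.004 |
| Unobserved within-man deviation | 0.5 | 0.048 / 0.013 | 0.090 / 0.022 | 0.133 / 0.034 |
| Unobserved within-man deviation | 1 | 0.090 / 0.024 | 0.173 / 0.048 | 0.243 / 0.064 |

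With slope 0, both analyses are within 0.004 of zero. A second simulation, recruiting until 29 complete with about 6 of 35 men leaving and slope 1 on the recorded response, gave completers-only bias of 0.156 at ρ 0.5 and 0.088 at ρ 0.7, against 0.015 and 0.009 with all visits.

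For scale, the SE of a meal contrast with 29 completers is √(2 × 2.8² × 0.5 / 29) = 0.52 at ρ 0.5, or 0.53 with period in the model. The largest bias is 0.243/0.53 = 0.46 of that SE, and 0.243/0.5 = 0.49 of the smallest worthwhile change.

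**The case against.** The strongest reply is that nothing in the protocol excludes withdrawers from the primary comparison. The sentence is permissive and sits in a paragraph on attendance and withdrawal. Twenty-nine completers is a recruitment target, not an analysis population. Analysis sets and model terms are commonly left to a SAP, which may exist. This stands in part: a reader might infer that the protocol declares a completers-only analysis, and it does not. What remains is that the one role it does assign is exploratory. A SAP that put these visits in the primary analysis would sit awkwardly with that sentence.

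The second reply is that recruiting to 29 completers already protects the planned precision, so withdrawers' visits are a gain above plan. That stands, and it is the main reason the priority is low. Reminders and compensation may also keep withdrawals few.

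The third is that the selection argument has no figures behind it. That also stands: the slopes are assumed, participants are blinded, and the near-zero bias of the mixed model holds only where leaving depends on recorded data.

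The fourth is that, under non-inferiority, an all-visits analysis should not simply displace the completers' analysis, and that visits affected by ineligibility or a significant deviation should not enter automatically. Both stand, and the fix below allows for them.

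**Conclusion.** The point holds as a low-priority correction. The protocol assigns withdrawers' data at most an optional exploratory role, and the natural consequence is that valid within-man contrasts already collected are left out of the primary comparison. The likely gain from using them is about 1-5% lower variance with one or two withdrawers giving two or three meals, rising to about 11% with five giving three meals. Using them also guards against selection where leaving is related to the recorded response, and reduces the bias without removing it where leaving depends on unobserved response.

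A reader might go further and conclude that the primary result will be biased, or that this rule leaves the trial short of its planned size. The protocol supports neither. It gives no dropout rate and no link between leaving and response; if the two are unrelated there is no bias, and the 29 completers are secured either way. The mmol/L figures rest on an SD that does not describe the LCPUFA outcome, so they show scale only.

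**What to change.** Replace the sentence on withdrawers under Randomisation and Blinding with wording such as:

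> *Data from men who leave early are retained unless the man asks for deletion. Their completed meal visits that supply the 4-hour change enter the primary analysis, using a model that accommodates incomplete crossover data (for example, a mixed model with meal and period as fixed effects and participant as a random effect). Visits at which a man was ineligible or had a significant protocol deviation do not enter on this basis alone; their handling is decided blind to results. Because the framework is non-inferiority, an analysis of men who completed all four meals is reported alongside, and the two are checked for consistency.*

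Keep 29 completers as the recruitment target. The mixed model is an example; the essential change is that evaluable visits have a stated place in the primary analysis.

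**Cost.** A protocol amendment notified to the ethics committee and the registry, with a check that the consent wording agrees. At five samples per visit, each withdrawer adds 2 × 5 = 10 or 3 × 5 = 15 fatty acid assays, against 29 × 4 × 5 = 580 for the completers. The fractions are already separated at the visit, and no extra participants are needed.
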